4.3.1. Informed Consent

The written informed consent form must be approved by the IRB/REB and adhere to ICH GCP and the ethical principles that have their origin in the Declaration of Helsinki.

The investigator is responsible for obtaining written informed consent from each subject, or if the subject is unable to provide informed consent, the subject's legally acceptable representative, prior to beginning any study procedures and treatment(s). The investigator should inform the subject, or the subject's legally acceptable representative, of all aspects of the study, including the potential risks and benefits involved.

All screening evaluations must be completed and reviewed to confirm that subjects meet all eligibility criteria prior to study enrollment. A screening log will be maintained to record details of all subjects screened and to confirm eligibility or record reasons for screening failure, as applicable.

The subject should be given ample time and opportunity to ask questions prior to deciding about participating in the study and be informed that participation in the study is voluntary and that they are completely free to refuse to enter the study or to withdraw from it at any time, for any reason. The informed consent must be signed and dated by the subject, or the subject's legally acceptable representative, and by the person who conducted the informed consent discussion.

A copy of the signed and dated written informed consent form should be given to the subject or the subject's legally acceptable representative. The process of obtaining informed consent should be documented in the patient source documents using the PRO-FRM-013: Documentation of Informed Consent. See Section 12.1.3 for detailed information on informed consent process.

4.4. Screen Failures

Individuals who do not meet the criteria for participation in this study (screen failure) may be rescreened. Rescreened Subjects should be assigned the same subject number as for the initial screening.

4.5. Availability for Follow-up

Patients must be accessible for treatment and follow-up. Investigators must assure themselves the patients randomized on this trial will be available for complete documentation of the treatment, adverse events, and follow-up.

4.6. Ability to tolerate current treatment

Patients must be able to maintain a stable position to tolerate SUPR or VMAT.

Protocol number v12.0; 16 Apr 2024

4.7. Biopsy/Tissue/Blood banking

N/A

Protocol number v12.0; 16 Apr 2024

4.8 Schedule of Assessments

Assessment	Screening: Visit-1	Baseline, Enrollment, Randomization: Visit 1	Treatment: Visit 2 (Day 1)	Treatment / Follow-Up (for 8Gy/1# patients) Visit 3 (Day 5)	Follow-Up Visit 4 (W2 post last RT) +/- 3 days	Follow-Up Final Visit (W4 post last RT) +/- 3 days
Informed Consent	X					
Inclusion/Exclusion Criteria	X					
Enrollment/ Randomization		X				
*Medical History/ Comorbidities	X					
Physical Examination	X					
€Pregnancy Test	X					
Patient Diary (provided to patient)			X	X		
**Brief Pain Inventory		X	X		X	X
**Functional Living Index - Emesis		X	X	X	X	X
PROMS		X	X		X	X
Treatment Related Data			X			
***Baseline & Follow-up		X	X		X	X
EQ-5D-5L		X			X	X

*may be done within 90 days, or 3 months, prior to enrollment

**BPI, FLIE and PROMS on Day 1 does not need to be repeated if collection was done within 7 days of first treatment (day 1).

***Baseline & Follow-up form does not need to be repeated if collection was done within 2 days of first treatment (day 1). If RT starts 3 or more days after baseline collection, or anytime medication changes (if known), this form will need to be repeated

€Urinalysis or serology – per institutional guidelines.

Protocol number v12.0; 16 Apr 2024

4.8.1 Investigations Prior to Randomization/Study Entry, During Trial and Follow-up

Physical and Medical History will be valid within 6 weeks prior to enrollment.

Pregnancy test results will be valid for 4 weeks prior to treatment.

5. Subject Treatment Plan

5.1. Trial Treatment Summary

5.1.1. ARM 1 - SUPR

Radiation Treatment Plan for SUPR (Arm 1)

- Planning according to local protocols.
- No more than 2 fields; no beam modifying devices, other than multileaf collimators (MLCs). Alternate weighting of beams allowed (ie. 1:2 AP:PA). Review of dosimetry not required, if performed as per institutional standard.
- Minimum of kV image matching on unit daily.

5.1.2. ARM 2 - VMAT

Radiation Treatment Plan for VMAT rapid (Arm 2)

Contouring:

GTV: based on available imaging (GTV may be based on CT sim scan alone. No special imaging) and is expected to be between 1.5 cm and 20 cm clinically or from diagnostic imaging

CTV is optional in all scenarios: when using CTV = GTV + 0.5 to 0.7 cm (RO preference), adjusted to the anatomy as further outlined below.

- In case of only bone involvement: recommendation is **not** to expand past bone; however, a 0.5 – 0.7 cm CTV expansion outside of bone and into muscle or soft tissue is allowed at the treating RO's discretion.
- In case of bone and soft tissue involvement: a 0.5 to 0.7 cm CTV expansion is optional and allowed at RO's discretion.
- In case of spinal metastases: CTV is optional and if used can encompasses whole vertebral body as per RO's discretion

PTV = CTV or GTV (if CTV not used) + (1 to 1.5) cm as per RO / centre preference.

PTV_eval = PTV cropped 0.5 cm below skin.

OAR's: A maximum of 2 OAR's are permitted for the VMAT arm. OAR contouring and constraints are at the discretion of the treating RO. However, if lung/kidneys are within 5 cm of the PTV, the absence of constraints for these contours should be documented in the treatment plans or dose constraint sheet prior to planning. PTV can be compromised for OAR at radiation oncologist's discretion. Kidneys are considered 1 organ.

Planning:

- AAA or other type-2 / model-based calculation framework
- Heterogeneities on
- Maximum calculation grid size = 2.5 mm
- Planning VMAT flash is permitted but not required
- Jaw-tracking is permitted but not required
- A normal tissue constraint should be used to control conformity to at least the 65% isodose level
- For the VMAT arm, up to two arcs are permitted
- The 80% conformity index (CI).

Required Constraints:

- PTV / PTV_eval coverage: The volume of the PTV covered by the 95% isodose volume must be greater than or equal to 98% ($V95\% \geq 98\%$). ($V95\% < 98\%$ minor violation; $V95\% < 50\%$ major violation).
- The 80% conformity index (CI), being the ratio of the 80% isodose volume to the PTV volume, must be less than 1.75 (1.75 - 1.9 minor violation; > 1.9 major violation)
- Plan maximum dose (Dmax) = 110% (> 110% but $\leq 115\%$ minor violation; > 115% major violation)
- Maximum of 2 constrained OAR's
- In case of accomplished constraints for CI, Dmax and OAR's (if present): no further plan modification permitted by RO

Suggested Constraints

Recommended OAR constraints are given on the table below, which are based on QUANTEC, adapted to the specific dose per fraction of the two schedules. The decision to include or adjust these constraints is at the discretion of the RO.

	8 Gy in 1 fraction	20 Gy in 5 fractions
*Spinal Cord (PRV)	Max dose < 110% of 8 Gy	Max dose < 110% of 20 Gy
Lungs (excl. GTV)	V6 Gy < 35%	V12 Gy < 35%
	Mean dose < 6 Gy	Mean dose < 12 Gy
Kidney (each)	V6 Gy < 30%	V12 < 30%
	Mean dose < 5 Gy	Mean dose < 10 Gy
**Small Bowel	Max dose < 110% of 8 Gy	Max dose < 110% of 20 Gy

* spinal cord to L2, spinal cord PRV is 0.5 cm margin around the spinal cord

** small bowel contoured by RO or RT depending on institutional policies

Plan Review and QA:

No pre-treatment dosimetric review is required if both the required and specified OAR constraints are met. Otherwise, the plan must be reviewed by the RO prior to treatment. Document any further plan modification secondary to subsequent local QA procedures as a minor protocol violation. Physics and dosimetry checks are to be performed as per local standard-of-care.

Verification Imaging:

IGRT: Minimum IGRT is daily 2D kV matching. CBCT is not required but may be used at the discretion of the treating radiation oncologist

Quality Assurance

Dosimetric compliance with protocol constraints will be evaluated by the planning dosimetrist(s) and physicist(s). Plan review by the radiation oncologist is not required for both arms. The radiation oncologist might review the plan but no plan modification at that point is permitted.

For VMAT, patient-specific QA should be performed per standard processes.

Institutional quality assurance rounds may also evaluate the radiation plans.

5.1.3. Duration of Study

The study is expected to be 7 years, as per section 3.3

5.2. Data Handling and Recordkeeping

- All subject data relating to the study will be recorded on printed or electronic CRF unless transmitted to the sponsor or designee electronically (e.g., laboratory data). The investigator is responsible for verifying that data entries are accurate and correct by physically or electronically signing the CRF.
- The investigator must maintain accurate documentation (source data) that supports the information entered in the CRF.
- The investigator must permit study-related monitoring, audits, REB review, and regulatory agency inspections and provide direct access to source data documents.

Protocol number v12.0; 16 Apr 2024

- Monitoring details describing strategy (e.g., risk-based initiatives in operations and quality such as Risk Management and Mitigation Strategies and Analytical Risk-Based Monitoring), methods, responsibilities and requirements, including handling of noncompliance issues and monitoring techniques (central, remote, or on-site monitoring) are provided in the SUPR-3D Monitoring Plan.
- The sponsor or designee is responsible for the data management of this study including quality checking of the data.
- The sponsor assumes accountability for actions delegated to other individuals (e.g., Contract Research Organizations).
- Study monitors will perform ongoing source data verification to confirm that data entered into the CRF by authorized site personnel are accurate, complete, and verifiable from source documents; that the safety and rights of Subjects are being protected; and that the study is being conducted in accordance with the currently approved protocol and any other study agreements, ICH GCP, and all applicable regulatory requirements.
- Records and documents, including signed ICFs, pertaining to the conduct of this study must be sent to the Study Principal Investigator (SPI) for long-term storage and will be retained by the SPI for 25 years after study completion. No records may be destroyed during the trial and/or retention period. No records may be transferred to another location or party without written notification to the sponsor.

5.2.1. Subject Reported Outcomes – Questionnaires

5.2.1.1. Functional Living Index – Emesis

To assesses primary efficacy outcome - Patient Reported Quality of life related to Radiation Induced Nausea and Vomiting (RINV), as scored by the FLIE at day 5 post RT start. Electronic or Paper both available.

5.2.1.2. Brief Pain Inventory

To assess pain flare and response. Electronic and Paper both available.

5.2.1.3. Patient Diary

To assess control of RINV and medication use. Paper version only will be provided to patient.

5.2.1.4. PROMS Questionnaire

Patient reported, combined questionnaire including:

- Single item from EORTC QLQ C-15 PAL (How would you rate your overall quality of life during the past week?) to assess overall quality of life
- PRO-CTCAE to assess fatigue and skin burn
- PRO-ECOG to assess functional status

Electronic or Paper both available.

5.2.1.5 EQ-5D-5L

To capture patient-reported Health-Related Quality of Life (HRQoL), scores from which will be used to inform cost effectiveness analysis of SUPR vs. VMAT.

5.2.1.6 Baseline Symptoms and Post-Treatment Toxicity

Baseline Symptoms and Post-Treatment Toxicity assessed by care provider at baseline and follow-up.

5.2.2 Records Retention

Records and documents, including signed ICFs, pertaining to the conduct of this study must be sent to the Study Principal Investigator (SPI) for long-term storage and will be retained by the SPI for 15 years after study completion. No records may be destroyed during the trial and/or retention period. No records may be transferred to another location or party without written notification to the sponsor.

5.3. Lifestyle Considerations, Prohibited Food and Additional Restrictions

5.3.1. Required Therapy

All patients will receive a 5HT-3 receptor antagonist (e.g. Ondansetron) as antiemetic prophylaxis prior to RT start

5.3.2. Permitted Concomitant Therapy

Nausea prophylaxis

Dexamethasone may be given for nausea prevention, though is not mandated.

Analgesics

Analgesics are allowed to be prescribed as needed by the patient to obtain optimal pain control.

Concurrent hormonal therapy

Concurrent receipt of hormonal therapy is allowed during this study.

5.3.3. Prohibited Concomitant Therapy

Use of the following concomitant therapies is prohibited as described below:

- Use of chemotherapy schemes containing potent enhancers of radiation damage (e.g. gemcitabine, doxorubicin, bevacizumab, adriamycin) are **discouraged within the first month after radiation**.
- WBRT in the 4 weeks before first RT and 4 weeks after last RT
- SFRT for brain metastases in the 4 weeks after last RT

5.3.4. Herbal Therapies

Concomitant herbal therapies that the subject is using do not need to be recorded.

5.3.5. Data for Concomitant Medications

Concomitant medications must be recorded on the SUPR-3D concomitant medication form, which is a cumulative form to be updated throughout the study.

If no concomitant medications are being taken at the time of study visits, this can be indicated on a line on the form, with the following annotation:

Protocol number v12.0; 16 Apr 2024

‘Confirmed no concomitant medications are being taken during study visit X [Date: DD MMM YYYY; INITIALS]’

5.4. Co-enrolment and/or Re-enrolment

Enrolment in other studies may be permitted. Investigators must check with study principal investigator.

Patients who have participated in the SUPR-3D trial previously, and completed all study visits, may be eligible for re-enrolment in to SUPR-3D. Sites must check with either the Site PI or Study PI regarding re-enrolment as all eligibility criteria must be met for the re-enrolment. Re-enrolled patients must be assigned a new study ID (treat as if new enrollment).

5.5. Subject Compliance/Deviations

Subject compliance, such as attending study visits and completing questionnaires, will be monitored via REDCap. If any visits are not completed, investigator or delegate must call and conduct follow-up over the telephone. Missed visits must be documented in the deviation log.

Deviations to eliminate immediate hazards to study subjects must be reported to the Study PI immediately upon discovery and to the REB within 7 calendar days. All other reportable deviations must be reported to the Study PI immediately, however to the REB within 15 calendar days. See section **12.1.2 Protocol Deviations** for a list of deviations.

Protocol number v12.0; 16 Apr 2024

6. Dose Modifications

N/A.

7. Assessment of Efficacy

Treatment Response Evaluation

FLIE:

Scores on all individual questions will be weighted equally, reversed if required and summed to create an overall FLIE score. Minimum score and maximum score will be 18 and 126 respectively. A low score is favorable, reflecting less nausea and vomiting.

The paper version of the FLIE is a 7-point Likert-scale. Patients' responses will be rounded to the closest point on the scale for entry in the digital database. I.e. if the response is 1.4, this will be rounded to 1. If the response is 1.5, it will be rounded to 2.

RINV:

Complete control: no increased episodes of nausea or vomiting with no increased use of anti-emetic medication from baseline

Partial control: 1-2 increased episodes of nausea or vomiting with no increased use of anti-emetic medication compared to baseline

Uncontrolled response: 3 or more increased episodes of nausea or vomiting, or increased use of anti-emetic medication from baseline

Overall control: includes complete and partial control

Pain:

Complete response: pain score of 0 at treated site with no increase in analgesic intake (stable or reducing analgesics in daily oral morphine equivalent (OMED).

Partial response: pain reduction of 2 or more at the treated site on a scale of 0 to 10 without analgesic increase, or analgesic reduction of 25% or more from baseline without an increase in pain.

Pain progression: Increase in pain score of 2 or more above baseline at the treated site with stable OMED, or an increase of 25% or more in OMED compared with baseline with the pain score stable or 1 point above baseline.

Indeterminate response: Any response that is not captured by the complete response, partial response or pain progression definitions¹⁴.

8. Assessment of Safety

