2.1. Trial Rationale and Background

Bone metastases are the most common site of distant metastases and can cause severe and disabling effects, including pain, spinal cord compression and pathologic fracture^{1, 2}. These complications can greatly affect a patient's quality of life and cause immense suffering.

Radiotherapy (RT) is an effective treatment for palliative patients with painful bone metastases. It is also efficacious in preserving function and maintaining skeletal integrity, while minimizing the occurrence of adverse skeletal related events³. There is a significant amount of evidence showing that a single fraction (SF) of RT provides equivalent pain relief as multiple fractions (MF), which are associated with more acute toxicity, are less convenient for patients and costlier for the health care system^{1, 4, 5}. Therefore, SF-RT is encouraged, but 20 Gy in 5 fractions is also allowed in this study, though should be chosen only in patients with a complicated bone metastases by fracture, neurological deficit (e.g. spinal cord compression), or a large soft tissue component. In patients with advanced disease, management strategies focus on improving quality of life (QOL), rather than conventional endpoints such as survival⁶.

Rationale for Current Study

Currently, the standard of care in British Columbia for palliative patients with bone metastases is SUPR. In other jurisdictions, however, factors such as physician remuneration make other complex planning techniques more popular.

BC Cancer is publicly funded with no direct costs to patients. All RT in the province is provided by 6 centres where radiation oncologists receive an annual salary, which are independent of RT treatment technique and duration⁷. Due to the lack of financial incentive associated with a more complex RT plan, BC Cancer is a unique clinical setting to assess the use of VMAT versus SUPR⁷.

As facilities providing RT have gained more experience with VMAT and improvements to VMAT planning software have been made, the planning time required has been reduced⁸. Previously, approximately 2 weeks was required for a team at the BC Cancer to create a VMAT plan for a palliative patient with bone metastases; however, we hypothesize this can now be reduced to three days in settings with low dose prescription.

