3.1. Study Objectives and Endpoints

3.1.1. Objectives

Primary Objective

The primary objective is to compare patient-reported Quality of Life related to Radiation Induced Nausea and Vomiting (RINV) between standard palliative radiotherapy and VMAT.

Secondary Objective(s)

To assess rate of complete control of RINV, compare patient reported toxicity, and evaluate pain response. However, we hypothesize that there will be no difference in pain response between the two arms, because they are receiving the same dose.

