4.1. Inclusion Criteria

Subjects must meet all of the following criteria to be eligible for participation in this study:

- Age 18 or older
- Able to provide informed consent
- Clinical diagnosis of cancer with bone metastases (biopsy not required)
- Currently being managed with palliative intent RT to 1-3 RT fields for bone metastases, at least one RT field (PTV) must (at least) partly lie within T11-L5 or pelvis.
- ECOG Performance Status 0-3
- Patient has been determined to potentially benefit from 8 Gy or 20 Gy
- Radiation Oncologist is comfortable prescribing 8 Gy in 1 fraction or 20 Gy in 5 fractions RT for bone metastases
- Negative pregnancy test result for women of child-bearing potential
- The baseline assessment must be completed within required timelines, prior to randomization.
- Patients must be accessible for treatment and follow-up. Investigators must assure themselves the patients randomized on this trial will be available for complete documentation of the treatment, adverse events, and follow-up.
- For simplicity of planning, expected GTV should be less than 20 cm based on radiological or clinical evidence
- Patient must be prescribed a 5-HT3 receptor antagonist (e.g. Ondansetron) as antiemetic prophylaxis prior to RT start.
- Patient is able and willing to complete the quality of life questionnaires, and other assessments that are a part of this study, via paper or using REDCap if they provide their email address on the informed consent

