APPENDIX A – ELIGIBILITY CRITERIA

Eligibility Checklist

You must be able to circle Y (Yes) to all of the following:

Y / N : Age 18 or older

Y / N: Able to provide informed consent

Y / N: Clinical Diagnosis of cancer with bone metastases

Y / N: Currently being managed with palliative intent RT to 1-3 RT fields for bone metastases, at least one RT field (PTV) must (at least partly) lie within T11-L5 or pelvis

Y / N: ECOG Performance Status 0-3

Y / N: Radiation Oncologist is comfortable prescribing 8 Gy in 1 fraction or 20 Gy in 5 fractions RT for bone metastases

Y / N: Patient has been determined to potentially benefit from 8 Gy or 20 Gy

Y / N / NA: Negative pregnancy test result for women of child-bearing potential

Y / N: Patients must be accessible for treatment and follow-up

Y / N: Radiological or clinical evidence confirming GTV is expected to be less than 20 cm

Y / N: Patient will be/has been prescribed a 5HT-3 receptor antagonist (e.g. Ondansetron) as antiemetic prophylaxis prior to RT start.

Y / N: Patient is able and willing to complete the quality of life questionnaires, and other assessments that are a part of this study, via paper or using REDCap if they provide their email address on the informed consent

Exclusion Criteria

You must be able to circle N (No) to all of the following:

Y / N: Serious medical co-morbidities precluding radiotherapy

Y / N: Clinical or radiological evidence of spinal cord compression

Y / N: Solitary plasmacytoma

Y / N: Pregnant or lactating women

Protocol number v12.0; 16 Apr 2024

Y / N: Target volume cannot be encompassed by a single VMAT isocentre

Y / N: Custom mould room requirements (shells and other immobilization that is standard-of-care is acceptable)

Y / N: Greater than two organs-at-risk requiring optimization.

Y / N: Spinal cord in treatment field has already received at least >30 Gy EQD2

Y / N: Whole brain radiotherapy (WBRT) within 4 weeks of RT start and planned WBRT in the 4 weeks after last RT

Y / N: Implanted electronic device within 10 cm of the RT fields

Y / N: Prostheses in the axial plane of the target, or within 1 cm of the PTV out-of-plane

Y / N: Previous RT that requires an analysis of cumulative dose (i.e. sum plans or EQD2 calculations)

Y / N: Oral or IV contrast if the local standard-of-care requires compensation for this in planning.

Y / N: Patient requires treatment outside standard clinical hours

Protocol number v12.0; 16 Apr 2024

Protocol Signature Page

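### The complete-response rule for pain has no baseline condition and eligibility requires no pain, so a patient at pain 0 before and after RT on stable analgesics counts as a complete responder

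*Combined protocol and SAP*

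**What the plan says.** Section 7 (Assessment of Efficacy, Pain) sets four categories. The first reads "Complete response: pain score of 0 at treated site with no increase in analgesic intake", with a gloss that stable or falling daily oral morphine equivalent (OMED) satisfies the analgesic condition. It mentions neither a baseline score nor a reduction. The other two substantive categories refer to baseline:

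- Partial response requires "pain reduction of 2 or more at the treated site on a scale of 0 to 10 without analgesic increase", or an OMED cut of at least 25% without more pain.
- Progression is a rise in pain or in OMED from baseline.
- Indeterminate is whatever the other three leave over.

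On entry, section 4.1 asks for "Clinical diagnosis of cancer with bone metastases (biopsy not required"), for "Currently being managed with palliative intent RT to 1-3 RT fields for bone metastases" and for "Patient has been determined to potentially benefit from 8 Gy or 20 Gy". None of these is a pain criterion, and section 4.2 adds none. The Appendix A checklist follows the same line: "Y / N: Clinical Diagnosis of cancer with bone metastases".

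Section 3.1.2 lists pain response by BPI as a secondary endpoint. Section 3.1.1 states the expectation: "we hypothesize that there will be no difference in pain response between the two arms". Section 9.1 specifies intention-to-treat and t-tests of average scores. It gives no pain-evaluable subset and no method for comparing response categories.

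**The concern.** A response rate should count patients who improved. Under section 7 a patient can enter the numerator with no pain at the start, no pain at the end and no change in medication. Randomisation puts such patients in both arms in about equal shares. They add nothing to the contrast, but they dilute whatever difference exists among patients with pain.

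The direction matters because the protocol expects equal pain response. Counting everyone is often defended as conservative, but it is not conservative when the expected finding is no difference, since dilution moves the estimate towards that finding. A published response rate would also be hard to interpret if an unknown part of it came from patients who had no pain to relieve.

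**Working it through.** **1. Does any other part of the plan close the gap?** No. Sections 4.1 and 4.2 and Appendix A contain no pain item, section 9.1 defines no subset, and the indeterminate category cannot catch a patient who already meets complete response.

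**2. Applying the section 7 rules to individual cases:**

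| Pain, baseline to follow-up | OMED, baseline to follow-up | Category |
|---|---|---|
| 0 to 0 | 0 to 0 | Complete response |
| 0 to 0 | 30 to 30 | Complete response |
| 0 to 0 | 30 to 20 (cut of 33%) | Complete response |
| 0 to 0 | 30 to 40 (rise of 33%) | Progression |
| 0 to 1 | 0 to 0 | Indeterminate |
| 0 to 2 | 0 to 0 | Progression |
| 1 to 0 | 0 to 0 | Complete response |
| 1 to 1 | 30 to 20 | Partial response |

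The first two rows are the defect. The third is a complete response on a score that did not move, although the OMED cut is a genuine change under the protocol's own partial-response rule.

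**3. The plan's own figure.** The documents give no pain response rate, no share of pain-free patients and no power for pain. The only relevant figure is the total of 250 in section 9.2, which is based on FLIE: means 36 and 28, SD 16, alpha 0.05 (taken as two-sided), power 0.90, dropout 30%. Per arm, n = 2 × (1.960 + 1.282)² × 16² / 8² = 84.1, rounded up to 85. That is 170 in total, and 170 / 0.7 = 243. The t-based version gives 86 per arm and 246. So 250 reproduces, and it leaves 250 × 0.7 = 175 evaluable patients, or 87.5 per arm.

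**4. Dilution.** Let f be the share with baseline pain 0, p the response rate among patients with pain, and q the share of baseline-zero patients scored as responders.

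- Observed rate = (1 − f) × p + f × q
- Change in the rate = f × (q − p)
- Observed difference = (1 − f) × (pA − pB), when f and q are the same in both arms

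The values of f, p and q below are assumptions. With p = 60% and 45%, and q = 1:

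| f | Observed rates | Difference |
|---|---|---|
| 0 | 60.0% vs 45.0% | 15.0 points |
| 5% | 62.0% vs 47.8% | 14.3 points |
| 10% | 64.0% vs 50.5% | 13.5 points |
| 20% | 68.0% vs 56.0% | 12.0 points |
| 30% | 72.0% vs 61.5% | 10.5 points |

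For example, at f = 20%: 0.8 × 0.60 + 0.2 = 0.68, 0.8 × 0.45 + 0.2 = 0.56, difference 0.12.

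The inflation depends on q. At f = 20% and q = 0.5, the 60% rate falls to 0.8 × 0.60 + 0.2 × 0.5 = 58%. The difference is still 12 points.

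A second set, for complete response alone, assumes 20% vs 35% and q = 0.85. At f = 10% the rates are 26.5% vs 40.0%; at f = 20% they are 33% vs 45%. In the latter case 0.2 × 0.85 = 17 of the 33 points in the lower arm, about half, come from patients without baseline pain.

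**5. Power.** This uses a two-proportion normal approximation, two-sided 0.05, comparing all patients with those whose baseline pain is above 0:

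- 60% vs 45%, q = 1, 87.5 per arm: 0.47 vs 0.49 at f = 5%; 0.37 vs 0.43 at f = 20%.
- 20% vs 35%, q = 0.85, 88 per arm: 0.54 vs 0.59 at f = 5%; 0.37 vs 0.51 at f = 20%.

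Excluding baseline-zero patients gains power in these examples despite the smaller number. Power is low either way.

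**The case against.** The case against is strong on size and on how far the remedy should go.

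- **Few pain-free patients may enrol.** Section 2.1 says of RT, "It is also efficacious in preserving function and maintaining skeletal integrity", but this follows a sentence on painful metastases and reads as an added benefit. A reader might take the mention of fracture and soft tissue component in the same section as pain-free indications. They are given there as reasons for choosing five fractions over one. Section 3.2 also speaks of additional lesions being treated later if symptomatic. This stands: pain-free entry is allowed, but nothing shows that it is common.
- **Dilution needs a true difference.** Both arms receive the same dose. If pain response really is equal and baseline-zero patients are balanced, the contrast is unbiased and only the absolute rate changes. A reader might infer that a finding of no difference is built into the rule. The documents do not support that: no equivalence or non-inferiority margin is stated for pain, and even at f = 20% the assumed difference keeps 12 of its 15 points.
- **Low-score patients can respond.** A reader might infer that patients at baseline 0 or 1 have no valid route to response. A patient at 1 can reach 0, or qualify through an OMED cut. A patient held at 0 by analgesics who cuts OMED by at least 25% without more pain has responded under section 7. Dropping every baseline-zero patient would discard these responders.
- **The planned analysis is unclear.** Section 9.1 names only t-tests of average scores, so the power figures describe a comparison that the plan does not spell out.

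None of this removes the defect. The rule as written still credits an unchanged, pain-free patient with a complete response.

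**Conclusion.** The point holds as a defect in a stated rule, with an effect of unknown size. That the rule misclassifies 0-to-0 patients on stable analgesics follows directly from section 7 and the eligibility text and needs no assumption.

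The shrinkage by (1 − f) needs a true difference, and equal f and q across arms. Inflation of the rate needs q above p, which is likely for complete response when such patients stay at 0, but is not certain. Because f is not in the documents, the loss of 0.7 to 3 points from an assumed 15 (f = 5% to 20%) shows a range and is not an estimate.

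The change should be made because pain response is a declared secondary objective with a stated expectation of no difference. It does not touch the primary FLIE analysis.

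**What to change.** In section 7:

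1. Require a baseline pain score above 0 at the treated site for complete response.
2. Limit the response denominator to patients with baseline pain above 0 or on analgesics at baseline. Let baseline-zero patients on analgesics respond only through the existing rule of an OMED reduction of 25% or more without increased pain.
3. Report patients with baseline pain 0 and no analgesics separately, for progression and flare only.
4. Add a sensitivity analysis restricted to baseline pain of 2 or more, where partial response by score is attainable.

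The cost is a few sentences and a derived flag. The BPI is already collected at baseline (sections 3.2 and 4.8), and baseline OMED is already needed for the section 7 definitions. The flag uses only baseline data, so the restricted comparison remains a randomised one. The response denominator becomes slightly smaller; no visit, treatment or sample size changes. The rule should be fixed before the arms are compared on pain.
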